Referral for IPV further care will be managed in two ways. In settings of immediate risk to the patient there will be immediate outreach to hospital security and a nurse specialist providing IPV support to the Emergency Department. For lower-risk cases, patients are provided psychoeducation and offered a referral to a national hotline for counseling and support for IPV victims. In cases where the abuse of the victim is observed by children, the provider is reminded in the documentation tool to immediately refer the case to state child protective services, as required by law, and contact information was given.

To prepare clinics for participation, we will work with the Primary Care Service Line Director, clinical leaders in clinics and staff to implement the study. We will provide manuals, trainings and online education for clinic staff and providers. Online training will be integrated with MUSC's MyQuest staff education system. Educational materials will include tip sheets on intimate partner violence and how to implement screening procedures, video demonstration of EHR use, as well as videos demonstrating suggested scripting for interactions with patients. During the initial week of the roll out, Epic research support personnel will be available in the clinics to help providers learn to use software modifications and to answer questions. Provider support for in-person individual IPV-related training and case consultations will be provided by two experts in IPV training and management through-out the implementation and operation of the study.

Data Sources/Collection

All data will be collected within the Epic EHR system.

Outcome measurement

The primary outcome measure for the study is the rate at which patients were screened for IPV across the clinics. This outcome is calculated as the share of patients who completed PVS questions from all eligible patients. The secondary outcome is the rate at which patients at risk for IPV are detected by screening procedures. The patient is flagged positive if they are positive on one of the three PVS questions (Table 1). Other outcomes are the severity of risk (using Danger 5 risk assessment, ranging from 0 to 5) observed in patients, physician compliance with IPV management tools (measured as the rate of completion of follow-up decision templates, and the rate of referrals for post-visit counseling to a national hotline (a share from screened positive patients).

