Based on our current practice visit patterns for unduplicated visits by women between age 18 and 49 years, we will have approximately 34,000 eligible visits during the non-screening steps and 34,000 during the screening steps. We have assumed an annual IPV prevalence of 5.5% within the preceding year, based on rates reported by the CDC for SC [17], a screening completion rate of 95%, a 75% counselling rate for women who screen positive, and a 50% referral rate to the Hotline. Studies report the ability of screening to increase patient referral to services from a 2.5 percentage point to an 8.0 percentage point increase based on current referral rates between 0% and 3.6% [18]. Based on an analysis of our archival data, we expect that our current referral rate for IPV for women aged 18-49 seen in our clinics is no more than 0.14% and that this rate will increase to 3.9% with screening.

With about 600 relevant patient visits over 6 months per clinic, 8-12 clinics per wedge, and 3 wedges, we estimate that we will have 97% power to detect an increase in screening (i.e. 0.14% vs. 5.5%), and 89% power to detect a difference in the rate of referral for counseling and/or calls to the Domestic Violence Hotline (i.e. 0.14% vs. 3.9%). While we may be somewhat overpowered for our primary analysis, these numbers of clinics and patients will also allow us to make very precise estimates of the treatment effects within relevant patient subgroups (e.g. whites vs. blacks, urban vs. rural) and to determine whether there are any differential impacts of the intervention on those subgroups. These power calculations are conducted using PASS15 (NCSS, Kayesville, UT) and verified using the 'steppedwedge' function in STATA (StataCorp, College Station, TX), assumed an intraclass correlation coefficient of 0.05 (to account for a moderate level of clustering of patients within clinics), along with an alpha of 0.05 and two-sided testing.

Statistical analysis

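### The 97% power for screening compares a referral rate with IPV prevalence, so the primary outcome, PVS completion, has no stated power and no control-period rate

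*Combined protocol and SAP*

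**What the plan says.** The Outcome measurement section defines the primary outcome: "This outcome is calculated as the share of patients who completed PVS questions from all eligible patients". The secondary outcome is the rate at which screening detects women at risk. A further outcome is "the rate of referrals for post-visit counseling to a national hotline (a share from screened positive patients").

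The Power Calculations section lists its inputs: "We have assumed an annual IPV prevalence of 5.5% within the preceding year", then "a screening completion rate of 95%, a 75% counselling rate for women who screen positive, and a 50% referral rate to the Hotline". On the baseline it expects that "our current referral rate for IPV for women aged 18-49 seen in our clinics is no more than 0.14"%, rising to 3.9% with screening. It then claims "97% power to detect an increase in screening (i.e. 0.14% vs. 5.5"%). For referral, where the contrast is 0.14% against 3.9%, the claim is "89% power to detect a difference in the rate of referral for counseling and/or calls to the Domestic Violence Hotline". It describes the trial as having rather more power than the primary analysis needs. The figures come from PASS15 and were "verified using the 'steppedwedge' function in STATA", with an intraclass correlation of 0.05 and two-sided alpha of 0.05.

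**The concern.** A power statement for a primary outcome needs that outcome's rate in each condition. Here both rates belong to other quantities. The one completion rate in the section, 95%, is an input to the 3.9% and is never used as an endpoint rate. No completion rate is given for the control periods, so a reader cannot say what the 97% is power for.

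The omission matters beyond the wording. Study design/Participants describes the control screen as a nurse's checklist based on judgment, without standardized questions. If control completion of the PVS is close to zero, power is not the issue, and the question becomes how a logit model handles a condition with no events. If completion of either screen was meant, power depends on a nurse-led completion rate that the plan does not report.

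**Working it through.** **What each rate is**

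- 0.14%: current referral rate (upper bound, archival data).
- 5.5%: assumed annual IPV prevalence.
- 5.5% x 95% = 5.2%: expected detection among all eligible women, on the plan's inputs.
- 5.5% x 95% x 75% = 3.9%: counselling among all eligible women. This reproduces the stated 3.9% and shows that the 95% enters only there. The 50% hotline rate is not used.
- 95%: expected PVS completion under intervention. Control rate: not given.

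**Reproducing 97% and 89%**

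Inputs from Power Calculations: 28 clinics, 600 visits per clinic per six months, intraclass correlation 0.05, two-sided 0.05. Figure 1 gives four periods and three steps. The clinics per step are given only as 8-12, so I assume 9/9/10.

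*Parallel comparison, 14 against 14 clinics.* Design effect = 1 + 599 x 0.05 = 30.95. Effective n per arm = 14 x 600 / 30.95 = 271.4. For 0.14% against 5.5%, SE = sqrt[(0.0014 x 0.9986 + 0.055 x 0.945) / 271.4] = 0.01402, z = 0.0536 / 0.01402 = 3.82, and power = Phi(3.82 - 1.96) = 96.9%. For 3.9%, SE = 0.01197, z = 3.14 and power is 88.1%. Across pooled or unpooled variance and 600 to 2,429 visits per clinic (68,000 / 28), the ranges are 96.5% to 97.2% and 87.6% to 88.9%.

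*Stepped wedge.* Generalized least squares on clinic-period proportions with period effects, an identity-scale approximation to the planned logit model. The covariance of a clinic's four means is p(1-p) x [0.05r J + {0.05(1-r) + 0.95/600} I], where J is the all-ones matrix, I the identity, and r is the between-step correlation divided by the within-step correlation. Power = Phi(z - 1.96).

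| r | Variance taken at | 0.14% vs 5.5% | 0.14% vs 3.9% |
|---|---|---|---|
| 1 (one clinic effect) | mean rate | z = 22.8, > 99.99% | z = 18.8, > 99.99% |
| 1 (one clinic effect) | intervention rate | z = 16.5, > 99.99% | z = 13.7, > 99.99% |
| 0.5 (assumed) | mean rate | > 99.9% | 99.8% |
| 0.5 (assumed) | intervention rate | 99.0% | 94.2% |
| 0.325 (chosen to fit) | intervention rate | z = 3.85, 97.0% | z = 3.18, 88.9% |

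With r = 1 and splits 8/8/12, 12/8/8 and 8/12/8, z is at least 16.1 and 13.3. Two different calculations therefore come close to both stated figures, and the plan's text does not separate them.

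**Detection.** Using 5.2% in place of 5.5% against 0.14% changes little: z = 16.1 to 22.1 with one clinic effect, and 95.8% in the parallel calculation. The baseline matters more. In the parallel calculation, 5.5% against an assumed control positive-screen rate of 1% gives 84%, and against 2% gives 57%.

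**Completion against 95%**

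- *PVS only.* Control completion is about 0%, inferred from the description of the control screen. The contrast is near-certain under either calculation. Control clinic-periods number 9 x 1 + 9 x 2 + 10 x 3 = 57 of 112, that is 34,200 of 67,200 visits. If none holds an event, lowering every period effect and raising the treatment effect by the same amount leaves the intervention cells unchanged and makes the control cells more likely, whatever the clinic effect. The likelihood then has no finite maximum for the treatment effect.
- *Either screen.* At assumed nurse-led completion of 80% or 90%, the stepped wedge with r = 1 gives z of at least 26.4 or 11.7. The parallel calculation gives 97.4% at 85% and 60.0% at 90%, so both the nurse-led rate and the correlation need to be stated.

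**The case against.** The strongest reply is that little hangs on this. The completion contrast is likely to be overwhelming, the mislabelled contrast is conservative if one clinic effect is used, and Figure 1 ends the last step in Q4 2021, so restated power cannot change recruitment. That limits the consequence, but it does not supply a power statement or a control rate for the primary outcome.

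Four stronger readings are tempting and are not supported:

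- *The stepped-wedge verification was not done, or a parallel formula was used.* A parallel calculation does come close, but so does a stepped wedge with a between-step correlation of about one third of the within-step value. One clinic effect is the analysis model in the Statistical analysis section; the power section does not say that it was the power input.
- *The 89% contrast is equally mismatched.* It is broadly like with like. Its baseline is a referral rate, and its endpoint is worded to cover counselling referral, hotline calls or both, so 3.9% is a natural value without the 50%. What remains is the denominator: all eligible women here, screen-positive women in Outcome measurement. Nor can one say that referral will only be described, since the analysis of other outcomes is said to be mainly, not wholly, descriptive.
- *The planned primary model will fail.* That holds only if control PVS completion is zero, which is inferred and not stated. It is also a point about the model, not about power.
- *The trial is underpowered.* Nothing in the documents shows this. The lower figures above rest on assumed rates or on a calculation that is not the trial's design.

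It is also fair to say that the primary definition, read literally, is PVS completion. Counting either screen is an alternative that the sponsor may have had in mind, and the definition does not offer it.

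**Conclusion.** The point holds as a mislabelled power statement. The 97% is not power for the primary outcome, and it does not fit the secondary outcome as written either: the baseline is a referral rate, and the intervention rate should be 5.2% on the plan's own inputs. Power and a control-period rate for PVS completion are missing. This rests on the plan's own labels and needs no assumption.

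The size of the power discrepancy does rest on an assumption. It is 97% and 89% stated against more than 99.99% for both with one random clinic effect, and it disappears at a between-step ratio of about 0.325 with variance at the intervention rate. The origin of the stated figures cannot be identified. The referral denominator is a smaller inconsistency.

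**What to change.** (a) Withdraw the 97% as power for the primary outcome and state the control-period completion rate. If the definition is meant literally, say that control PVS completion is about 0% by construction and that the contrast with 95% is near-certain, and report it as a risk difference or descriptively in place of a logit treatment effect. If completion of either screen is meant, say so, take the nurse-led completion rate from archival EHR data and give power against 95%.

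(b) Relabel 0.14% against 5.5% as detection, replace the baseline with the control positive-screen rate, use 5.2% under intervention, and rerun.

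(c) Label 3.9% as counselling among all eligible women and reconcile its denominator with the referral outcome in Outcome measurement.

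(d) State the between-step correlation and the number of clinics per step used in the calculation.

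Cost: one paragraph and a rerun of the power program, with possibly one sentence of the model in Statistical analysis. Clinics and patients do not change.

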We will use a generalized linear mixed model with a logit link controlling for block set and a fixed effect for each step, as discussed by Hussey and Hughes [19], to compare active screening accounting for the cluster design with a random clinic effect. Primary analyses will also adjust for patient characteristics (age, race) since these have been associated with risk of IPV. Models will be estimated with interaction terms to assess subgroup effects for specific patients, and to examine the effect of practices' characteristics on the heterogeneity of the estimates.

The intraclass correlation coefficients will also be estimated and reported for screening and counselling to assess the assumptions made for the sample size analyses so that this information will be available to future investigations using similar designs and outcomes.

Analysis for the other outcomes will be largely description. Frequency tables with patient demographics, including race, insurance, ethnicity, age, and marital status will be reported. Responses to individual PVS questions will also be presented in the form of frequency tables. Danger 5 risk assessment will be presented using histogram showing counts of patients that scored 0 to 5 of the risks [16]. Physician compliance will be measured as percentage of screened positive patients for whom decision-support templates have been based. Rates of referrals will be reported as percentage from total of patients screened positive.

In addition, we will perform sensitivity analyses to assess the effects of early vs. late randomization, potential “learning” effects that may occur as the screening becomes better integrated in practice routines, the effect of the practices’ presence of a IPV champion prior to the study, and the effect for practice-specific screening refusal and rate of counselling acceptance on the overall estimate. Sensitivity analyses for the primary and secondary outcomes will be conducted using several methods, which have different missing data assumptions: 1) Complete case analyses which assumes missing data are completely at random; 2) Multiple imputation using $M=10$ imputations, which assumes missing at random; and 3) Assigning contrasting age group, race and income category classifications for missing values differentially by intervention group, which aligns with non-ignorable missingness (the data missingness is nonrandom and related to the actual values.)

Follow-up interview

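### The 89% power is for a between-condition referral contrast among all eligible women, but the plan only reports referral as a percentage of screen-positive women

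*Combined protocol and SAP*

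**What the plan says.** Power Calculations claims "89% power to detect a difference in the rate of referral for counseling and/or calls to the Domestic Violence Hotline", using 0.14% versus 3.9%, two-sided alpha 0.05 and an intraclass correlation of 0.05. The control figure is introduced with the statement that "our current referral rate for IPV for women aged 18-49 seen in our clinics is no more than 0.14" percent, and the same rate is then expected to rise to 3.9%. Both rates therefore have all women of eligible age as their denominator. The stated inputs are a 5.5% annual prevalence and "a screening completion rate of 95%, a 75% counselling rate for women who screen positive, and a 50% referral rate to the Hotline".

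Outcome measurement puts referral in the third tier, after the primary and secondary outcomes, and defines it as the "rate of referrals for post-visit counseling to a national hotline (a share from screened positive patients" (parenthesis closed in the source). The Intervention section describes the same event: lower-risk patients are "offered a referral to a national hotline for counseling and support for IPV victims".

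Statistical analysis specifies one comparative model, a logistic mixed model with step effects, "to compare active screening accounting for the cluster design with a random clinic effect". A later paragraph makes the other outcomes mostly descriptive and reports referral as a percentage of screen-positive patients. Counselling appears in two more places: "The intraclass correlation coefficients will also be estimated and reported for screening and counselling", and a sensitivity analysis on practice-specific refusal and "rate of counselling acceptance on the overall estimate".

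**The concern.** The power statement and the analysis plan differ in two respects. The denominator changes from all eligible women to screen-positive women. The type of inference changes from a two-sided between-condition test to a reported percentage. A percentage of screen-positives in the intervention periods cannot yield the difference that was powered.

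A reader will take 89% power as a commitment to test whether the intervention raises referral. The rest of the document encourages this. The abstract says each component's efficacy gets its own assessment, the Background names patient referral within the third component, and the Discussion cites initiation of counselling as an evidence gap. If event, denominator and model stay open, they can be chosen after the data are seen.

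**Working it through.** **Inputs (Power Calculations).** 28 clinics; 68,000 visits, 34,000 per condition; about 600 visits per clinic per six months; prevalence 5.5%; completion 95%; counselling 75% of screen-positives; Hotline referral 50%, denominator not stated; control referral 0.14%; ICC 0.05; two-sided alpha 0.05.

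**1. Reproducing the 89%.**
- Visits per clinic: 68,000 / 28 = 2,429.
- Design effect: 1 + (2,429 − 1) × 0.05 = 122.4.
- Effective size per condition: 34,000 / 122.4 = 278.
- Two-proportion test with pooled variance: 0.14% vs 3.9% gives 88.5% (stated 89%); 0.14% vs 5.5% gives 97.0% (stated 97%).

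Two other parallel-cluster set-ups come close: 8,400 visits per condition at 600 per clinic gives 87.8% and 96.7%; 16,800 at 1,200 per clinic gives 88.3% and 96.9%. All three use all eligible visits as the denominator, so the 89% is a power for the all-women contrast.

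**2. Stepped-wedge check.** The Hussey–Hughes variance is I·s²(s² + Tτ²) / [(IU − W)s² + (U² + ITU − TW − IV)τ²].
- Clinics split 8/10/10 (assumed, within the stated 8-12) over four periods: I = 28, T = 4, U = 54, W = 1,172, V = 122. The bracketed coefficients are 340 and 860.
- Total variance at 3.9%: 0.039 × 0.961 = 0.03748; τ² = 0.05 × 0.03748 = 0.001874; s² = 0.95 × 0.03748 / 600 = 0.0000593.
- Standard error 0.00277; (0.039 − 0.0014) / 0.00277 = 13.6, so power is about 100%.

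The problem is therefore one of specification, not sample size.

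**3. What was powered and what will be reported.**
- Screen-positives: 0.055 × 0.95 = 5.225%; × 34,000 = 1,777 (assuming no net misclassification by the PVS).
- Control referrals: 0.0014 × 34,000 = 48.

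| Event | Rate among all women | Number | Share of screen-positives |
|---|---|---|---|
| Counselling | 5.225% × 0.75 = 3.92% | 1,332 | 75% |
| Hotline, 50% of screen-positives | 5.225% × 0.50 = 2.61% | 888 | 50% |
| Hotline, 50% of counselled women | 3.92% × 0.50 = 1.96% | 666 | 37.5% |

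Only the counselling row gives the plan's 3.9%, while the outcome as defined is Hotline referral. That 3.9% was built this way is an inference from the match. Nothing says that the archival 0.14% counts counselling.

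**4. Could the shares be compared between conditions instead?** The documents give no nurse-led detection rate. As an assumption, let it run from 0.14% to 5.5%. The control share, 0.14% divided by that rate, then runs from 100% to 2.5%. Even the direction of a difference is not fixed, and no power can be computed for it.

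**5. Precision of the planned percentage.** 1,777 / 28 = 63.4 per clinic; design effect 1 + 62.4 × 0.05 = 4.12. The 95% half-width, 1.96 × √[q(1 − q) × 4.12 / 1,777], is 4.1, 4.7 and 4.6 points at q = 0.75, 0.50 and 0.375. Without clustering it is 2.0, 2.3 and 2.3 points.

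**The case against.** The phrase about active screening may name the condition rather than the outcome, since the power section speaks of screening and non-screening steps. The mixed model would then not exclude referral. The other outcomes are only mostly descriptive, and the planned ICC for counselling is meant to check the sample-size assumptions. This leaves room for a referral model but does not specify one: the text handles referral separately, as a percentage of screen-positives, with no comparison and no all-women denominator.

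The power sentence names a composite of counselling and/or Hotline. If Hotline referrals are a subset of counselled women, the composite is exactly 3.9%, and the 2.6% and 2.0% figures test a reading that the sentence does not make. That is fair, and the event point is secondary. What remains is that the defined outcome is Hotline referral only and that the content of the 0.14% is not given. Under the stepped-wedge variance, power stays near 100% at all three rates.

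Table 1 defines positives for both screens, so the denominator might include nurse-led positives. However, Outcome measurement flags patients by the PVS, and step 4 shows that a mixed denominator would not recover the powered contrast.

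It is also true that separate assessment of components does not promise a between-condition test, that referral is a third-tier outcome, and that the ICC of 0.05 is borrowed for the precision figure.

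**Conclusion.** The inconsistency holds with high confidence. The 89% describes a control-versus-intervention difference among all eligible women, about 48 versus 1,332 events per 34,000 visits. The plan specifies only a percentage among about 1,777 screen-positives. No specified analysis carries the stated power.

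The ambiguity about the event (3.9% against 2.6% or 2.0%) is inferred from the arithmetic, and the main finding does not depend on it. The counts rest on the plan's own prevalence and completion rates and on no net misclassification by the PVS. The primary and secondary outcomes are not affected. This should be corrected, because the document offers a powered referral result that its analysis section does not deliver.

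**What to change.** Reconcile Outcome measurement, Power Calculations and Statistical analysis in one of two ways.

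**(a) Specify the comparison.** Add a referral endpoint with all eligible women as denominator and one stated event, either Hotline referral alone or counselling and/or Hotline, that the EHR captures in both conditions. Analyse it in the stepped-wedge mixed model already planned. Restate the control and expected rates for that event, give the denominator of the 50%, and recompute power with the stepped-wedge variance. Keep the share among screen-positives as a descriptive process measure. If the endpoint is added after the data were seen, label it post hoc.

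The cost is one extra model and a data source for control periods. Counselling may be recorded less completely there, because the Navigator that documents it is part of the intervention. The restated effect may be less favourable.

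**(b) Withdraw the claim.** Delete the 89% and state that referral is descriptive. Expected precision can be given instead: about ±4 to 5 points at an ICC of 0.05, or about ±2 points if clustering is ignored, marking the ICC as an assumption for this outcome. This is a wording change; the cost is that no powered referral claim remains.

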A lack of expertise of primary care providers in the assessment of risk and difficulty linking patients to needed resources may also pose significant barriers for providers in screening processes. Integrated tools for risk assessment and referral for follow-up of positive IPV screening, including reminders of legal conditions that may mandate disclosure (for example, children witnessing IPV events), may help providers feel more comfortable with screening tasks [5, 10], and thus encourage compliance with screening guidelines. While screening and counseling for IPV is a billable activity, the desire to keep discussions private may result in a provider not using IPV-related billing codes and losing potential credit for time spent counseling in provider productivity calculations. An approach to document time spent in confidential activities that a health system might *choose not to bill for* because of privacy concerns may be important positive reinforcement for provider screening behaviors for IPV.

The objective of this paper is to describe the protocol of a stepped wedge cluster randomized trial for evaluating the effectiveness an IPV screening workflow consisting of three major components:

1. a non-interruptive alert for annual IPV screening;
2. PVS confidential screener;
3. Provider risk assessment of PVS screening results and patient referrals.

Stepped wedge study design was chosen for several reasons [11]. Firstly, we had a background control condition present (nurse-led screening) in all clinics. Secondly, because each cluster acts as its own control we need a limited set of clusters to reach the desired level of statistical power. We also needed time to do staff trainings and intervention support, and make sure that they follow our intervention protocol, with stepped wedge design we could do trainings in 5 clinics at a time. In addition, this design gives us control over temporal trends in the data.

METHODS/DESIGN

Study design/Participants

The protocol for this study is based on a stepped wedge cluster randomized controlled trial design [12].

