28 clinics (14 Family Medicine, 12 Internal Medicine Primary Care and 2 women's health clinics) are grouped into 3 blocks each holding 8-12 clinics based on number of eligible patients seen in 2018-2019 and the number of full-time employees in clinics to assure that each block has similar population and employee size. We then use random number generator to randomize the starting time for 3 blocks. The target population is all women aged 18-49 who visit the clinics during the whole study period. Multiple screenings of the same patient can be made as it is described in the Intervention section. The blocks are shown in Figure 1.

Control (nurse-led screen)	Intervention Start (nurse-led and confidential screen)		
Time Period 0	Time Period 1	Time Period 2	Time Period 3

Q1 2020 – Q2 2020	Q3 2020 – Q4 2020	Q1 2021 – Q2 2021	Q3 2021 – Q4 2021
28 clinics	8-12 clinics 16-20 clinics	16-20 clinics	28 clinics

Figure 1. Randomized Stepped Wedge design with 28 clinics.

The control condition is a nurse-led screen developed by MUSC and deployed in 2019. When patients are roomed in all outpatient clinics, nurses complete a checklist where they, based on professional judgment (e.g., without asking standardized questions), screen for a variety of factors. One of those factors is Abuse/Neglect. Clicking on this item in the Epic EHR user interface, opens a second menu for nurses to document either the absence of any evidence of abuse/neglect or the presence of different risk factors. Selecting the “caregiver degrades or threatens patient”, “abuse/neglect suspected”, “evaluation for abuse”, “excessive fear/withdrawn or guarded behavior” or “has unexplained injuries or bruises” was considered a positive screener for spousal abuse risk. It is important to note that control screening is always present (though not necessarily completed) when patient is eligible for confidential screening intervention, thus two screens are working at the same time during intervention period.

IRB determined that this was a quality improvement effort which did not require consent identifying and managing IPV is part of current practice the intervention was the Epic automatic fielding and special protection approaches used that decreased patient risk of disclosure.

Intervention

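### The model's single constant screening effect and lone clinic intercept leave the reported effect size exposed to drift with time since switch-on, and its interval exposed to clinic-specific drift

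*Combined protocol and SAP*

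**What the plan says.** Statistical analysis specifies "a generalized linear mixed model with a logit link controlling for block set and a fixed effect for each step", "accounting for the cluster design with a random clinic effect". Age and race are added, and interactions are planned for patient subgroups and practice characteristics. No term for time since switch-on, no clinic-by-step term and no small-sample or robust standard error is mentioned.

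The same section lists "sensitivity analyses to assess the effects of early vs. late randomization" and potential learning "effects that may occur as the screening becomes better integrated in practice routines", but gives no model for either.

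The last paragraph of Background says that "this design gives us control over temporal trends in the data". Under Study design/Participants the 28 clinics "are grouped into 3 blocks each holding 8-12 clinics", with four half-year steps and every clinic on the intervention in the last one. Power Calculations gives one ICC (0.05) and no between-step correlation. On the primary outcome, Outcome measurement says: "This outcome is calculated as the share of patients who completed PVS questions from all eligible patients".

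**The concern.** With staggered starts and no control clinics in the last step, a constant-effect model compares newly started clinics partly with clinics already on the intervention. If the effect depends on how long a clinic has been running, the single coefficient need not be an average of the true effects. The plan foresees such a change: it names learning effects, and the Intervention section says "During the initial week of the roll out, Epic research support personnel will be available in the clinics".

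Separately, step effects shared by all clinics remove only common trends. If clinics move differently from step to step, a clinic intercept alone treats that movement as information about the intervention.

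At stake are the reported size of the effect and the width of its interval.

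**Working it through.** **Inputs from the documents.** 28 clinics, 3 blocks of 8-12, 4 steps (Study design/Participants). About 600 visits per clinic per step, ICC 0.05, two-sided alpha 0.05, and contrasts 0.14% vs 5.5% and 0.14% vs 3.9% with stated power 97% and 89% (Power Calculations). **Assumed, not in the documents:** the effect paths and the between-step correlations. Age and race are left out of the check.

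**1. The plan's own power.** 34,000 / 14 = 2,429 visits per clinic; design effect 1 + 2,428 × 0.05 = 122.4. A parallel comparison of 14 vs 14 clinics then gives 97.0% and 88.5%, matching the stated figures. The Hussey-Hughes stepped-wedge formula gives over 99.9% for both. Detecting the planned effects is not the difficulty.

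**2. What the constant effect averages (linear scale).** With x = 1 for intervention and 0 for control, and equal blocks, each block-step mean gets the coefficient (x - block mean of x - step mean of x + 1/2) / (5/6), where 5/6 is the sum of squares of the numerators.

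| Block | Step 0 | Step 1 | Step 2 | Step 3 |
|---|---|---|---|---|
| First to start | -0.3 | 0.5 | 0.1 | -0.3 |
| Second | 0 | -0.4 | 0.4 | 0 |
| Third | 0.3 | -0.1 | -0.5 | 0.3 |

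- First step since switch-on: 0.5 + 0.4 + 0.3 = 1.20.
- Second: 0.1 + 0 = 0.10.
- Third: -0.30.

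Over all 15 ordered splits of 28 clinics into blocks of 8-12 the weights are 1.18 to 1.23, 0.04 to 0.15 and -0.33 to -0.27; the second and third together are -0.23 to -0.18. With block fixed effects they do not depend on the ICC.

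For equal blocks, estimate = e1 - 0.2(e2 - e1) - 0.3(e3 - e2). If the effect starts at d and changes by g per step, this is d - 0.5g, while the true effects run from d to d + 2g. A constant effect is recovered without bias.

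**3. The planned logit model at 0.14% vs 5.5%** (fitted to expected counts, blocks of 9, 9 and 10):

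| Share of 5.5% reached, by step since switch-on | True odds ratios | Reported |
|---|---|---|
| 100/100/100% | 42/42/42 | 42 |
| 90/95/100% | 37/39/42 | 35 |
| 80/90/100% | 33/37/42 | 28 |
| 50/75/100% | 20/31/42 | 13 |
| 100/95/90% | 42/39/37 | 45 |
| 100/90/80% | 42/37/33 | 48 |
| 100/75/50% | 42/31/20 | 66 |

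One natural yardstick is the 3:2:1 average of the log odds ratios, since the three exposure steps are seen in 3, 2 and 1 block-steps. For 50/75/100% it is (3 ln 20 + 2 ln 31 + ln 42) / 6 = 3.27. The report is ln 13 = 2.56. The gap of about 0.70, with a standard error near 0.22, is about 3 standard errors. For 80/90/100% the gap is about 1, and for 90/95/100% about 0.5. In simulations of the 50/75/100% path, the 95% interval missed this average in 76-82% of runs (83-92% in reverse order). A model with exposure-step indicators and a clinic-by-step effect missed it in 2-5%.

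**4. Clinic-specific drift.** On the linear scale, true over reported standard error = √(1 + 600 × ICC × (1 - r) / (1 - ICC)), where r is the between-step correlation. At ICC 0.05 and r = 0.95: √(1 + 600 × 0.05 × 0.05 / 0.95) = √2.58 = 1.6. At r = 0.9 and 0.8 it is 2.0 and 2.7. At ICC 0.01 the three ratios are 1.1, 1.3 and 1.5.

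On the logit scale, an ICC of 0.05 can mean a clinic variance of 0.173 (latent scale: 0.05/0.95 × π²/3) or 0.820 (proportion scale at 5.5%). Simulated error of the planned model's 95% interval, constant effect, r = 0.95/0.9/0.8:

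| Rates | Variance 0.173 | Variance 0.820 |
|---|---|---|
| 0.14% in both | 5-7% | 5-7% |
| 0.14% vs 5.5% | 6/6/5% | 9/12/21% |
| 5.5% in both | 7/11/19% | 25/36/51% |

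The Monte Carlo standard error is up to 2.5 points. Separate runs with variance 0.173 and r = 0.8 gave coverage of 96% at 0.14% vs 5.5%, 79% at 5.5% in both and 59% at 30% vs 50%. Adding a clinic-by-step effect with t on 25 degrees of freedom gave 2-6% error in the scenarios tried. The t reference alone did not repair the planned model (16% and 47% at 5.5% in both, r = 0.8).

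**The case against.** Several objections stand and limit the point.

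- A reader might infer that any steady drift pushes the logit estimate outside the true range. It does not. With control at 50% and intervention rates of 95/90/85%, the true odds ratios are 19/9/5.7 and the model reports 18.1, which is inside. The exceptions found occur when rates fall from near the ceiling.
- Drift by calendar step is different. The step weights are 0.5, 0.1 + 0.4 = 0.5 and -0.3 + 0 + 0.3 = 0, so on the linear scale the estimate stays inside. In the logit model, odds ratios of 20/31/42 by calendar step report 24, and the reverse order reports 38. A model with exposure-step indicators would then show a spurious duration trend (26, 27, 29 in the rising case).
- A reader might take the standard error to be known to be wrong. That rests on correlations that the documents do not give, and at the plan's own contrast with the smaller variance the error is nil. The plan nowhere posits 5.5% in both conditions.
- The plan also provides training before launch and expert support throughout, and it already lists learning and early-vs-late analyses. The case for steep drift is therefore not strong. What remains is that these analyses have no stated model.
- An exposure-time average costs precision, and the 3:2:1 weighting is one choice among several.

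**Conclusion.** The point holds in limited form. Under effects that change steadily with time since switch-on, the constant-effect estimate lies outside the range of true effects on the linear scale, and also in the planned logit model at the plan's low rates. The error is small for mild drift (about 0.5-1 standard error) and large only if uptake roughly doubles or halves. The standard error is too small if clinics drift differently: near nil with both conditions at 0.14%, 5-6% or 9-21% interval error at 0.14% vs 5.5% depending on the clinic variance, and substantial with both conditions near 5% or with more common outcomes.

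The documents do not support reading this as a threat to significance at the planned effects.

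Nor does it reach the primary outcome as written. Nurse-led control screening contains no PVS questions, so control completion is near zero and the log odds ratio has no finite value until that definition is settled. The point concerns outcomes that control clinics can score, such as detection as defined in Table 1. The section does not say explicitly whether the secondary outcome gets this mixed model.

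**What to change.** For each modelled outcome that control clinics can score:

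- Add a random clinic-by-step effect to the planned logit mixed model, use a t reference on about 25 degrees of freedom (28 clinics minus 3 blocks), and report the within-step and between-step ICCs.
- Specify the planned learning analysis as the same model with indicators for the first, second and third step since switch-on. Report the three effects and one pre-specified average beside the constant-effect estimate. State that this model assumes the effect depends on exposure time and not on calendar time.
- State that, if the exposure-step effects differ, the constant-effect estimate will not be interpreted as an average effect.
- Limit the Background claim on temporal trends to trends common to all clinics.

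Settle the definition of the PVS completion outcome first.

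Making the exposure-time average the primary estimate is the sponsor's choice. For the 3:2:1 average, the standard error is 1.35-1.40 times that of the constant-effect model at similar rates, and 1.9-2.3 times at 0.14% vs 5.5%. The reason is that few control events are expected in the last step with control clinics (10 × 600 × 0.0014 = 8.4). No new data are needed. The cost is SAP wording, wider intervals and occasional fitting failure at very low rates: with both conditions at 0.14%, 4 of 600 fits of the larger model gave no usable estimate.
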